Alcohol Biosensor Monitoring for Alcohol Related Liver Disease

NCT03533660

June 15, 2022

Study Protocol and Statistical Analysis Plan

A. Specific Aims - Alcohol Biosensor Monitoring for Alcohol Related Liver Disease

Successful treatment of alcoholic liver disease (ALD) depends primarily on total abstinence from alcohol. Patients are instructed to maintain complete abstinence in order to have the best health outcomes and prevent ALD sequela or worsening of their liver disease. Different than addiction treatment where abstinence or even harm reduction may be an eventual goal with less need for immediate adherence, the complete abstinence requirement in this patient population makes it a useful model in which to test new strategies for efficient monitoring of patient behavior. Currently monitoring of ALD patients' alcohol use is primarily done through clinical interview and conventional laboratory alcohol testing. Optimally patients would be interviewed frequently and randomly tested, although in real world clinical settings this is difficult to accomplish. Continuous monitoring of alcohol use by wearable biosensors is possible but to date these devices have not been used in clinical medical settings to monitor adherence to medical directives. For ALD patients such devices could facilitate monitoring of alcohol abstinence providing both patients and clinicians with real-time information that may be critical for development and adjustment alcohol treatment plans.

From our prior work (K23 AA00257 and R01 DK066266) we determined that most discoveries of alcohol use in ALD patients are not made until months after the initiation of consumption and were largely captured based on prospective repeated multi-method research measures not routinely employed in a clinical setting. Continuous alcohol monitoring in the months following a hospitalization for ALD could provide more accurate appraisal of alcohol use that when combined with feedback may motivate patients to change drinking habits and engage in appropriate treatment intervention. Whether biosensor devices would facilitate identification beyond self-reports, be integrated into the clinical workflow, accepted by clinicians and patients, and improve outcomes requires investigation. Recent technology advancements expand continuous biosensor performance while reducing overall cost. It could be assumed that monitoring with a biosensor would be more convenient and more desirable, but there could be disadvantages. Patients may feel uncomfortable using the device or feel it is an intrusion. Clinicians may find additional data cumbersome or not useful to care delivery.

Therefore feasibility of integrating such technology into routine clinical care requires examining both patients' and clinicians' perceived potential benefits (e.g., patient convenience, clinician confidence in data and its value, potential improvement in care delivery, facilitation of developing/adjusting treatment plans, reduction in staff burden) and possible barriers (e.g. patient resistance to adoption, disruption of clinician workflow or established communication). These process considerations are essential to guide the development of a full scale trial and future translation into clinical practice. Thus the convenience, feasibility and acceptability of such devices require vetting by patients and clinicians alike. Our R21 proposal targets NIAAA PA 15-301 Alcohol Use Disorders: Behavioral Treatment, Services and Recovery Research soliciting proposals for co-morbid medical and alcohol use disorders, specifically proposals using technology to develop and validate assessments capturing real-time data to use in clinical treatment paradigms.

We propose a 3 month RCT pilot of alcohol biosensor monitoring (ABM)(WrisTAS-see methods) for patients with a recent hospital discharge for ALD decompensation. Patients who intend to stop drinking will wear the ABM and be randomized to receive ABM personalized feedback on the data retrieved from the device (ABM) vs. an enhanced usual care group that will wear the ABM device but not receive information about device data (EUC). Considering future translation into medical practice we chose a monthly assessment schedule aligned with the typical ALD clinical follow up and chose the EUC group to most closely resemble a typical medical encounter where generic questions on alcohol use are asked. The study will also include quantitative and qualitative data collected from participants and 15 clinical stakeholders (e.g. physicians, nurse practitioners, care coordinators) who will provide opinions on ABM usability, acceptability, feasibility, and potential to change clinical care and outcomes. Qualitative methods are especially useful for understanding patient and clinician cultures and perspectives to determine the perceived needs, barriers, and preferences for monitoring alcohol use and are essential for future translation of this technology into clinical practice.

Specific Aim 1. To determine usability, acceptability, feasibility and efficiency of ABM for ALD patients.

Specific Aim 2. To determine whether ABM plus feedback improves outcomes for ALD patients who intend to stop alcohol use compared to EUC. Hypotheses 1-5: ABM will 1) reduce alcohol use (primary outcome), and 2) improve readiness for alcohol abstinence, 3) improve self-efficacy, 4) improve initiation of addiction treatment and 5) reduce ALD related hospital admissions and ER visits (secondary outcomes).

Specific Aim 3. To explore with clinicians whether ABM data is useful, acceptable, feasible and efficient.

This study will inform our development of a full scale project by 1) determining the potential for and value to ABM healthcare integration 2) identifying barriers to ABM implementation 3) determining long term wearability of ABM devices and 4) determine whether identified patient outcome effect sizes appear clinically meaningful to justify ABM monitoring and evaluation in a full-scale randomized controlled trial in the clinical environment.

D. Approach: Research Design and Methods

We address the NIH mandate for rigor and transparency (NOT-OD-16-011) in the proposal and Table 1.

Inclusion: ≥ 18 years old, willing to accept randomization, and agree to wear device for 3 months.

Consistent with findings from alcohol treatment seeking individuals in NIAAA's Project MATCH⁵⁹ we will enroll ALD patients with SOCRATES problem recognition subscale score >26 (scores ≤ 26 indicate very low recognition). Maisto⁶⁰ suggests individuals with low recognition in the face of secondary alcohol complications may have pathological denial or cognitive impairment and these individuals are unlikely to intend to stop use.

Table 2. STUDY PROCEDURES

Recruitment, screening

- Prior to discharge from ALD hospitalization patients will be approached by CLD staff
- After CLD staff receive verbal consent, study coordinator will contact and screen patients (SOCRATES recognition subscale >26). If subject meets screening criteria they will be consented and enrolled

Randomization and baseline assessment

- Subjects will be randomly assigned 1:1 ratio ABM with feedback or EUC (permuted blocks to limit assignment imbalances across enrollment). All subjects wear ABM (WrisTAS)
- Random assignment implemented using sequential, opaque, numbered envelopes opened by the study coordinator who will inform the subject. Investigators/assessors blinded to allocation
- Baseline assessments completed-Form90 AI, SOCRATES, AASE, AWR, DrInC, DPI (Table 3)

Monthly ABM feedback and EUC procedures (see Appendix A) and data collection (Table 3)

- ABM –receives monthly typical CLD medical appointment clinic questions plus personalized feedback on downloaded ABM drinking data, risk/referral information, and patient brochures if alcohol use reported
- EUC –(attention control) monthly typical CLD medical appointment clinic questions including self-report alcohol questions, risk/referral information and patient brochure provided if alcohol use reported
- Issues with comfort or adjustment of WrisTAS will be addressed
- See methods & 4.1.5. data safety monitoring for quality control procedures monitoring intervention fidelity
- 6 week mid-point assessment on study outcomes-Form90 AI, SOCRATES, AASE, AWR, DrInC, DPI

Final Assessment procedures

- Repeat of baseline measures-Form90AF, SOCRATES, AASE, AWR, DrInC, DPI (Table 3), TAM2
- Qualitative interview on feasibility, acceptability, usability (Appendix B)
- 15 CLD clinicians complete TAM2 and INT questionnaires and have qualitative interview on feasibility, acceptability, usability, applicability to health care (Appendix B)

Exclusions: Non-English speaking (<5% CLD); persisting encephalopathy, MOCA scores <21 (moderate cognitive impairment) or neurologic diseases (e.g. Parkinson's), conditions which would affect survey assessments; patients with unresponsive acute alcoholic hepatitis, multi-organ failure, fulminant hepatic failure, or MELD score >21 (all with 3-month mortality $\geq 20\%$),^{61,62} cancer/terminal illness, non-cirrhotic conditions; those unable to wear a wrist monitor (e.g., edema); and those currently abusing drugs (checked by urine toxicology screen), lacking a residence, or unable to identify a contact person (if lost to follow-up).

Study design/methods for patient: (see Table 2 procedures): We will screen and enroll using above inclusion/exclusion criteria. We will

demonstrate the ABM device and note it must be worn at all times. We will use a 2-arm parallel groups design; subjects randomized 1:1 to either receive personalized feedback on the ABM data or receive enhanced usual care (EUC). The EUC group will have ABM data down-loaded for alcohol outcomes assessment but will not receive feedback on the data. *At each of 3 consecutive monthly sessions both groups will be asked standard medical questions (e.g. medications, symptoms). In addition the ABM feedback group will receive personalized feedback on downloaded data including graphical displays of alcohol use (Appendix A).* Our feedback script is based on standard personalized feedback interventions using key elements: personalized alcohol use information, comparison to normative cohort, risks of use, and resources for help.^{52,63,64} At the first visit (and at subsequent visits if use continues) both groups will receive information on negative health consequences, local alcohol addiction treatment referral information, and 2 NIAAA brochures on health consequences and treatment help (see scripted protocols Appendix A). EUC is “enhanced” because beyond generic alcohol use questions scripted information on risks and resources is not commonly provided. A research assistant blinded to assignment will perform outcome assessments at baseline, 6 weeks and final interview. Final assessments include quantitative and qualitative questions on perceived usability and device satisfaction, acceptability, lifestyle compatibility, and feasibility of long term use. So as not to pair participant payment with intervention, the payment schedule aligns with assessments but includes compensation for wearing the device.

For ultimate medical setting dissemination we use non-physician personnel because we see this as the future of such interventions. Medical technicians, increasingly used to extend clinical staff, are ideal for feedback delivery. *Our study uses medical technicians who will be assigned to only one arm of the study and separately trained to prevent cross-contamination. Drs. [name] and [name] will train them on protocol delivery using lectures, role playing, audiotaping and training cases using the designed feedback delivery sheet/printed materials provided to participants. During training we will elicit and address any challenges to the maintenance of fidelity. [name] will assess competence based on ratings following principles of treatment fidelity evaluation,^{65,66,67,68} to focus on adherence and competence to the structured, didactic style of sessions. To maintain session and assessment fidelity refresher training will occur midway through the enrollment period, and adherence, competence and reliability will be rated. For certification a random 20% of audiotaped sessions will be reviewed with retraining for deficiencies (see also DSMP 4.1.5.a Fidelity Development, Training, and Monitoring). Completed assessment and feedback sheets will be inspected for errors.*

Clinician participants: At study completion 15 CLD clinicians will review de-identified ABM data from the study and be asked a range of quantitative/qualitative questions on feasibility, acceptability, usability, graphical display of data, workflow integration, and potential health impacts (Appendix B) and be paid.

E. Analytic Plan

Specific Aims 1 & 3. To determine usability, acceptability, feasibility and efficiency of ABM for patients and clinicians. **Qualitative data coding and analysis:** De-identified transcribed interviews will be thematically coded¹⁰⁷ and a codebook developed for patients and clinicians. The constant comparison method will be used, and subsequent interviews may be modified/informed by findings from previous interviews to explore emerging themes as analysis proceeds. After initial consensus is reached among two coders, interviews will be coded by one coder and reviewed by at least one additional coder. Coding discrepancies will be resolved through consensus. Periodic interviews (expected rate, 1 in 8) will be coded by two coders independently as another check for inter-coder reliability. Further, interviews that have already been coded will be reviewed as more codes are identified. [name] will monitor for coding drift by periodically contrasting recent vs. earlier coded interviews. For **SA1&3** a summary of themes extracted from patient and clinician interviews will be prepared, with examples of interview quotes. We will also examine descriptive statistics on WrisTAS data including amount of time worn vs. removed and examine data for evidence of tampering to use as variable examining wearability and feasibility.

Specific Aim 2. Analyses will follow an intent-to-treat principal. We will first examine univariate distributions on baseline characteristics and on each outcome. We will examine the data for extent and pattern of missingness across outcome assessments. Potential violations of assumptions of planned parametric methods of analysis will be explored and resolved, e.g., variables will be transformed as needed; nonparametric methods will be employed if transformations are inadequate. Baseline demographic and clinical characteristics of the two study groups will be examined via χ^2 tests for categorical variables and t-tests for continuous variables (or Wilcoxon Rank Sum tests if necessary) in order to (a) describe the sample and (b) evaluate whether the randomization process effectively balanced the groups. If imbalances are observed, we

may need to adjust (covary) for significant and/or large baseline differences in the evaluation of hypotheses.

The primary outcome is alcohol use (H1), which we will test via 2 measures: % of days drinking; total quantity/frequency during period between downloads. Secondary outcomes (**H2-4**) are readiness for alcohol abstinence, self-efficacy, initiation with addiction treatment will be analyzed using SOCRATES subscales and AASE/AWR (continuous variables), **H5** Form 90AF hospital stays and ER visits (% of days hospitalized and no. of hospital admissions+ER visits). For each primary/secondary outcome, we will use a linear mixed effects model with fixed effects for intervention group (2 groups) and the repeated measures factor, time (pre-intervention, 6 weeks, and 3 mons post-intervention); and random effects for individual participant and intercept.

Statistical Power: Ours is an exploratory study; the ESs we might observe are unknown. For the simple effects we will compute as described above, with 30 participants in each of 2 groups being compared in a given test and alpha at .05, we would have power at 80% to detect an ES, $d \geq 0.76$. Brief feedback interventions can produce moderate to large ESs for reducing alcohol use and consequences (d of 0.6-0.8).^{81,111-113} Even if 5-8 participants are lost to attrition, we should have sufficient power to detect simple effects within the range found in previous feedback studies. Again, however, our interest will be to examine feasibility issues and ESs as opposed to testing for statistical significance.

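### Baseline adjustment is triggered by an observed imbalance instead of being pre-specified, which gives up precision at no saving; the gain may be negligible for the primary outcome

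*Combined protocol and SAP*

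**What the plan says.** All references are to the combined protocol and SAP.

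- **E. Analytic Plan, Specific Aim 2.** Baseline demographic and clinical characteristics are compared by chi-square, t or Wilcoxon tests, partly to judge whether randomisation balanced the arms. If it did not, the team "may need to adjust (covary) for significant and/or large baseline differences in the evaluation of hypotheses".
- **Same section, model.** Every primary and secondary outcome gets a linear mixed model with "fixed effects for intervention group (2 groups) and the repeated measures factor, time (pre-intervention, 6 weeks, and 3 mons post-intervention", and a random intercept for participant. No baseline covariate is listed.
- **Same section, outcomes.** H1 is percentage of days drinking and "total quantity/frequency during period between downloads". H2 to H4 use the SOCRATES subscales and AASE/AWR. H5 uses Form 90 "hospital stays and ER visits (% of days hospitalized and no. of hospital admissions+ER visits".
- **Same section, Statistical Power.** The target is introduced with "For the simple effects we will compute as described above", and the paragraph ends by saying "our interest will be to examine feasibility issues and ESs as opposed to testing for statistical significance".
- **Table 2, randomization and baseline assessment.** Allocation is 1:1 by "permuted blocks to limit assignment imbalances across enrollment", with no stratification factor named. The instruments are in hand at entry: "Baseline assessments completed-Form90 AI, SOCRATES, AASE, AWR, DrInC, DPI".

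**The concern.** Whether to adjust is decided after the baseline differences have been seen, under a rule with no threshold for a large difference and no named covariate. Allocation is not stratified on any stated factor, so balance on baseline drinking or readiness is left to chance in a sample of 60.

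Listing the pre-intervention value as a level of time may look as if it already uses baseline information. If the arms have their own means at every visit, it adds no precision to a follow-up comparison. If change from baseline is reported, it uses baseline inefficiently.

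The study's main quantitative product is a set of effect sizes that will help decide whether a full-scale trial is justified. What is at stake is how tightly they are estimated, and whether they depend on a choice made after looking at the data.

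**Working it through.** **Inputs.** 30 per arm, alpha 0.05 and prior effects of d = 0.6 to 0.8 come from the Statistical Power paragraph. A two-sided test, unit SD, approximately normal outcomes and complete data are assumed. The baseline-outcome correlation, rho, is not in the documents; 0.1, 0.3, 0.5 and 0.7 are assumed.

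**The plan's own figure.** The plan states 80% power for d of at least 0.76. A two-sample t-test with 30 per arm has 82.5% power at 0.76. The detectable effect at 80% power is 0.736 with 30 per arm and 0.762 with 28. The stated figure is thus reproduced, slightly conservatively, by a plain two-group comparison with no baseline adjustment.

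**Standard errors for one follow-up visit.**

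- Ignoring baseline: sqrt(2/30) = 0.258. Power at d = 0.6 is 63% and the 95% half-width is 0.52. Generalised least squares with three equally correlated visits and a group-by-time term gives the same 0.258 at every rho.
- Change from baseline: 0.258 × sqrt(2(1 − rho)).
- Adjusted for baseline: 0.258 × sqrt(1 − rho²). A model that constrains the arms' baseline means to be equal gives the same values.

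| rho | Change: SE, power | Adjusted: SE, power |
|---|---|---|
| 0.1 | 0.346, 40% | 0.257, 63% |
| 0.3 | 0.306, 49% | 0.246, 67% |
| 0.5 | 0.258, 63% | 0.224, 75% |
| 0.7 | 0.200, 84% | 0.184, 89% |

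Adjustment is at least as precise as change for any rho, because 2(1 − rho) − (1 − rho²) = (1 − rho)², which is never negative.

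**Cost of estimating the slope.** The adjusted formula treats the slope as known. Estimating it from 60 patients multiplies the variance by about 1 + 1/56 on average, so the SE rises by a factor of sqrt(57/56) = 1.009. At rho 0.1 this gives 0.257 × 1.009 = 0.259, marginally worse than no adjustment. Break-even is where 1 − rho² = 56/57, that is rho of about 0.13.

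**Attrition.** The plan allows for 5 to 8 lost without saying whether this is in total or per arm. If 8 are lost in total (26 per arm), power at d = 0.6 is 56% unadjusted and 60 / 69 / 84% adjusted at rho 0.3 / 0.5 / 0.7. If 8 are lost per arm (22 per arm), unadjusted power is 49%.

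**The trigger.** For one baseline variable with 30 per arm, a chance difference over 0.2 SD occurs in 44% of trials and a significant one in 5%. In about 39%, then, the difference exceeds 0.2 SD without being significant, and the written rule does not settle what to do. In those trials, adjusting or not moves the estimate by 0.09 / 0.16 / 0.22 SD on average at rho 0.3 / 0.5 / 0.7. Over all trials at rho 0.5, the SE is 0.250 if only significance triggers adjustment, 0.229 if over 0.2 SD also does, and 0.224 if adjustment is always made.

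**Which group contrast.** Suppose the true effect is 0.60 at both follow-up visits. In a group-plus-time model with a pre-intervention row, the group term averages over three visits, one of which cannot carry an effect: (0 + 0.60 + 0.60)/3 = 0.40. Averaging only the two follow-up visits recovers 0.60, with SE 0.258 × sqrt((1 + rho)/2) = 0.208 / 0.224 / 0.238 at rho 0.3 / 0.5 / 0.7. Baseline adjustment cuts this to 0.258 × sqrt((1 + rho)/2 − rho²) = 0.193 / 0.183 / 0.155.

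**The case against.** The best counter-argument is that little may be gained where it matters most. All patients enter after recent heavy drinking, and for H1 the only available baseline is self-reported while the outcome measured between downloads comes from the device. A weak correlation is plausible, and at rho 0.1 there is nothing to gain. This stands and limits the size of the point, though it does not apply equally to the questionnaire scales, which have their own baseline values.

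Second, a generous reading of the trigger costs little on average (0.229 against 0.224 at rho 0.5), and the shift in the undecided cases is below one standard error. This also stands. But no such reading is written down, and the calculation assumes that the variable in question predicts the outcome.

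Third, percentage of days drinking and admission counts may be far from normal. The plan already provides for transformation or nonparametric methods, so the figures above are a guide to scale only.

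A reader might also infer that the plan fails to define its reported effect, or that it will report the group term averaged over the pre-intervention visit. The documents do not support either. The power paragraph refers to simple effects described above it, which suggests that the contrast is set out in text not in the public document. It is also unclear that H1 has a pre-intervention row at all, since no device value precedes randomisation. Nor do the documents single out 3 months over 6 weeks.

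**Conclusion.** The point holds as a free improvement of minor weight. Adjustment that depends on observed imbalance is inferior to pre-specified adjustment for each outcome's baseline value. For the same contrast, adjustment has a smaller standard error than both the unadjusted difference and change from baseline at every assumed correlation from 0.3 to 0.7. The size rests entirely on a correlation that the documents do not give: negligible at 0.1, and a fall of about 29% in the standard error at 0.7 (0.184/0.258 = 0.71). It also assumes complete data and roughly normal outcomes.

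A reader might take the data-dependent rule to inflate type I error. That is not claimed. In simulation with one covariate and rho from 0.3 to 0.7, a fixed rule that adjusts only for significant differences rejected a true null in 3.6 to 4.8% of trials. The study is also an exploratory pilot that puts effect sizes ahead of significance tests.

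The definition of the contrast is a secondary request for clarification, not a demonstrated error.

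**What to change.** Replace the imbalance-triggered sentence with adjustment for the baseline value of each outcome, applied whatever balance is observed, and present the baseline table as summaries without tests. By outcome:

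- **H1:** baseline Form 90 drinking.
- **SOCRATES and AASE/AWR outcomes:** each scale's own baseline.
- **H5:** the matching baseline Form 90 item, if it is collected.
- **Any outcome with no baseline value**, which may include treatment initiation (H4): no covariate, stated in advance.

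Where a pre-intervention value of the same measure exists, a mixed model with the arms' baseline means constrained to be equal is an equivalent choice.

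As a clarification, state that the reported effect is a post-baseline group contrast with its 95% CI. It can be a named visit or the average of 6 weeks and 3 months, as the sponsor chooses.

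The cost is revised SAP wording and about one degree of freedom per model. It needs no new data, no larger sample and no change to the power statement.

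### The Aim 2 mixed model names no group-by-time term or contrast; reported as written, it dilutes the effect size for every outcome with a pre-intervention visit

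*Combined protocol and SAP*

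**What the plan says.** Section E, Specific Aim 2, gives one linear mixed model for all primary and secondary outcomes, with "fixed effects for intervention group (2 groups) and the repeated measures factor, time (pre-intervention, 6 weeks, and 3 mons post-intervention"), plus a participant random intercept. No interaction, visit-specific contrast, change score or baseline constraint is named. Baseline covariates are mentioned only as a possible response to observed imbalance.

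The Statistical Power paragraph begins "For the simple effects we will compute as described above" and gives 80% power for d of 0.76 with 30 per group and alpha .05. It adds "Brief feedback interventions can produce moderate to large ESs for reducing alcohol use and consequences (d of 0.6-0.8"), then "Even if 5-8 participants are lost to attrition, we should have sufficient power to detect simple effects", and closes by saying that "our interest will be to examine feasibility issues and ESs as opposed to testing for statistical significance". Nothing earlier in the supplied text describes simple effects.

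Table 2 shows which outcomes have a pre-intervention value: "Baseline assessments completed-Form90 AI, SOCRATES, AASE, AWR, DrInC, DPI", then "6 week mid-point assessment on study outcomes-Form90 AI, SOCRATES, AASE, AWR, DrInC, DPI", with the baseline measures repeated at the final assessment. One of the two primary alcohol measures is "total quantity/frequency during period between downloads", which points to the device. The source of the other, the percentage of days drinking, is not stated.

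**The concern.** A model with group and time but no interaction assumes one constant arm difference at all visits, including the visit before any feedback. Under randomisation that assumption is false whenever the intervention works. The single group coefficient then mixes a true zero with the follow-up effects. Such a model also cannot produce group differences by visit, which are the simple effects that the power paragraph relies on.

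The stake is the estimate more than the test. Section A says that the observed effect sizes will help decide whether a full-scale trial is justified. A diluted effect size could make a useful intervention look too small to pursue.

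**Working it through.** **Inputs from the documents:** 30 per arm; alpha .05 (sidedness not stated, two-sided assumed); d = 0.76; anticipated d of 0.6-0.8; loss of 5-8 participants; visits at pre-intervention, 6 weeks and 3 months.

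**Assumptions not in the documents:** within-person correlation rho of 0.1 to 0.7, equal SD (set to 1) at each visit, the time course of the effect, and random loss after baseline.

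**The plan's own figure.** A two-sided two-sample t-test at one visit with 30 per arm has noncentrality 0.76/√(2/30) = 2.94 on 58 df, so power is 82.5%. The d detectable with 80% power is 0.736, and 29 per arm would suffice for 0.76. The stated 0.76 is slightly conservative and fits a single-visit, two-group comparison.

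**What the stated model estimates.** With complete data, the group estimate equals the arm difference in participants' three-visit means. Fitted mixed models in 60 simulated trials agreed to within 1e-14. Hence

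E(group coefficient) = (0 + d6 + d3)/3.

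This does not depend on rho. For equal follow-up effects it is 2d/3:

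- d = 0.60: 0.40
- d = 0.76: 0.51
- d = 0.80: 0.53

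In a separate simulation of 400 trials (rho 0.5, true d 0.76), the coefficient averaged 0.52 and the group-by-3-month interaction 0.76.

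**Other time courses (illustrative), against the 3-month effect:**

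- 0.38 then 0.76: (0 + 0.38 + 0.76)/3 = 0.38, a 50% loss
- 0.8 then 0.6: 1.4/3 = 0.47, a 22% loss
- 0.8 then 0.4: 1.2/3 = 0.40, no loss

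**Other standardiser.** The SD of the three-visit mean is √((1+2rho)/3). Dividing 2/3 by it gives 1.05 at rho 0.1 (a 5% gain) and 0.75 at rho 0.7 (a 25% loss).

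**Attrition.** Suppose 8 participants in total (4 per arm) contribute only a baseline row. Generalised least squares then gives

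E = 26 × 2d / [26 × 3 + 4(1+2rho)].

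For d = 0.76 this is 39.52/82.8 = 0.48 at rho 0.1 and 39.52/87.6 = 0.45 at rho 0.7, a loss of 37% to 41%.

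**Power (secondary).** The group coefficient has variance (2/30)(1+2rho)/3. With d = 0.76 at both follow-ups:

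| rho | Group coefficient as written | Baseline-adjusted 3-month contrast (4000 simulated trials) |
|---|---|---|
| 0.1 | 86% | 82% |
| 0.2 | 81% | 83% |
| 0.3 | 75% | 86% |
| 0.5 | 66% | 92% |
| 0.7 | 58% | 98% |

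The middle column falls below 80% once rho exceeds about 0.21. With correlation 0.1 from baseline to follow-up and 0.5 between follow-ups, it is 79%. The baseline-adjusted contrast recovers 0.76 to 0.77 on average.

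**Device-only measure.** With two follow-up values and no baseline row there is no dilution: power is 95%, 92% and 88% at rho 0.3, 0.5 and 0.7.

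**The case against.** The strongest reply is that the power paragraph commits to simple effects, which in a repeated-measures design means group differences at a given time. The 0.76 figure also matches a single-visit comparison. On that reading the model sentence is incomplete and the authors never meant to report a pooled coefficient. This is probably what was intended. It still leaves the plan without the term that makes simple effects estimable and without a statement of which visit or contrast counts.

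The supplied text may also be abridged here: the power paragraph points back to a description that is not present, and reference numbers jump from 107 to 111. That lowers confidence somewhat, but it does not supply a contrast.

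Dilution is not established for the primary outcome. At least one of its measures appears to come from the device, and the percentage of days drinking is affected only if it is taken from Form 90. This stands, and limits the certain reach to SOCRATES and AASE/AWR.

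The one-third figure is conditional, as the time-course and standardiser results show, and the plan does not say whether the 5-8 losses are in total or per arm. The shift from 0.76 to 0.51 is also only about one standard error of a single-visit difference, √(2/30) = 0.26. But it is systematic, so the confidence interval would be centred in the wrong place.

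Finally, adding the interaction alone might be thought enough. It would remove the dilution. However, a change-from-baseline contrast has power of only 70%, 84% and 97% at rho 0.3, 0.5 and 0.7 (normal approximation, variance (2/30) × 2(1−rho)). Baseline adjustment, with variance (2/30)(1−rho²), gives 87%, 92.5% and 98.5%.

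**Conclusion.** The concern holds and should be fixed, with medium confidence because the authors probably intended an interaction. Followed literally, the stated model cannot give the visit-level effects that the power paragraph uses. For outcomes with a pre-intervention row, its group coefficient is (0 + d6 + d3)/3. Given complete data, equal follow-up effects and the single-visit SD as standardiser, the reported effect is one third too small. The loss against the 3-month effect ranges from nil to 50% over the time courses tried. The power figures rest on assumed correlations and matter less, since the plan disclaims significance testing. For a device-only measure the problem is different: the three-level time factor has no pre-intervention value to use.

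**What to change.** Replace the model sentence with wording such as:

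> The 6-week and 3-month values will be modelled with fixed effects for group, time, group-by-time and the baseline value of the outcome (or all three visits with baseline arm means constrained equal), and a random participant intercept.

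Then:

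- Name, before analysis, one primary contrast and one standardiser, reported with a 95% CI. The arm difference at 3 months is one example; the choice is the authors'.
- State whether the percentage of days drinking comes from the device or from Form 90.
- For a device-only measure, model the post-baseline periods only, with baseline Form 90 drinking as covariate.
- In the power paragraph, replace the reference to simple effects with the named contrast.

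The cost is SAP wording and one changed model statement. No new data, visits or participants are needed, because Form 90, SOCRATES, AASE and AWR are already collected at baseline.
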